16.3 Data & Safety Monitoring

16.31 Safety review

The principal investigator(s) and the study statistician will review the study monthly to identify accrual, adverse event, and any endpoint problems that might be developing. The Mayo Clinic Cancer Center (MCCC) Data Safety Monitoring Board (DSMB) is responsible for reviewing accrual and safety data for this trial at least biannually, based on reports provided by the MCCC Statistical Office.

16.32 Adverse Event Stopping Rules

Patients who report > grade 2 rash, pain, allergic reaction, or any other > grade 2 side effects attributed to the study medication will stop study drug/placebo and be monitored. Appropriate local care should be administered by the treating physician.

The PI has the right to discontinue this study at any time for reasonable medical or administrative reasons. The DSMB may also terminate study per early stopping rules.

16.4 Subset Analyses for Minorities

16.41 Study availability

This study will be available to all eligible patients, regardless of gender, race or ethnic origin.

16.42 Statistical analysis by subset

There is no information currently available regarding differential effects of this regimen in subsets defined by race, gender, or ethnicity, and there is no reason to expect such differences to exist. Therefore, although the planned analyses will look for differences in treatment effect based on racial groupings, the sample size is not increased in order to provide additional power for subset analyses.

16.43 Regional population

The geographical region served by MCCC has a population which includes approximately 3% minorities. Expected sizes of racial by gender subsets are shown in the following table:

Accrual Targets			
Ethnic Category	Sex/Gender		
	Females	Males	Total
Hispanic or Latino	2	2	4
Not Hispanic or Latino	18	18	36
Ethnic Category: Total of all subjects	20	20	40
Racial Category			
American Indian or Alaskan Native	1		1
Asian		1	1
Black or African American	2	2	4
Native Hawaiian or other Pacific Islander	1		1
White	16	17	33
Racial Category: Total of all subjects	20	20	40

Ethnic Categories: **Hispanic or Latino** – a person of Cuban, Mexican, Puerto Rican, South or Central American, or other Spanish culture or origin, regardless of race. The term “Spanish origin” can also be used in addition to “Hispanic or Latino.”

Not Hispanic or Latino

Racial Categories: **American Indian or Alaskan Native** – a person having origins in any of the original peoples of North, Central, or South America, and who maintains tribal affiliations or community attachment.

Asian – a person having origins in any of the original peoples of the Far East, Southeast Asia, or the Indian subcontinent including, for example, Cambodia, China, India, Japan, Korea, Malaysia, Pakistan, the Philippine Islands, Thailand, and Vietnam. (Note: Individuals from the Philippine Islands have been recorded as Pacific Islanders in previous data collection strategies.)

Black or African American – a person having origins in any of the black racial groups of Africa.

Native Hawaiian or other Pacific Islander – a person having origins in any of the original peoples of Hawaii, Guam, Samoa, or other Pacific Islands.

White – a person having origins in any of the original peoples of Europe, the Middle East, or North Africa.

17.0 Records and Data Collection Procedures

17.1 Submission Timelines:

Baseline information should be provided within 2 weeks of patient registration, while 2 and 4 week data should be provided within 2 weeks of patient submission of such.

17.2 CRF completion

This study will use Medidata Rave® for remote data capture (rdc) of all study data. Data collection for this study will be done exclusively through the Medidata Rave® clinical data management system. Access to the trial in Rave is granted through the iMedidata application to all persons with the appropriate roles assigned in Regulatory Support System (RSS). To access Rave via iMedidata, the site user must have an active account and the appropriate Rave role (Rave CRA, Read-Only, Site Investigator) on the organization roster at the enrolling site.

17.3 Site responsibilities

Each site will be responsible for ensuring that all materials contain the patient's initials, MCCC registration number, and MCCC protocol number. Patient names must be removed.

17.4 Overdue items

A member of the Mayo Clinic study team (e.g. Protocol specialist, data manager, PI, etc.) may contact site personnel via email regarding overdue forms and outstanding queries.

18.0 Budget

18.1 Costs charged to patient: routine clinical care

18.2 Tests to be research funded:

CBD cream & placebo will be provided from research funds.

Appendix I: EORTC QLQ-CIPN20 Instrument

ENGLISH

EORTC QLQ – CIPN20

Patients sometimes report that they have the following symptoms or problems. Please indicate the extent to which you have experienced these symptoms or problems during the past week. Please answer by circling the number that best applies to you.

During the past week :	Not at All	A Little	Quite a Bit	Very Much
31 Did you have tingling fingers or hands?	1	2	3	4
32 Did you have tingling toes or feet?	1	2	3	4
33 Did you have numbness in your fingers or hands?	1	2	3	4
34 Did you have numbness in your toes or feet?	1	2	3	4
35 Did you have shooting or burning pain in your fingers or hands?	1	2	3	4
36 Did you have shooting or burning pain in your toes or feet?	1	2	3	4
37 Did you have cramps in your hands?	1	2	3	4
38 Did you have cramps in your feet?	1	2	3	4
39 Did you have problems standing or walking because of difficulty feeling the ground under your feet?	1	2	3	4
40 Did you have difficulty distinguishing between hot and cold water?	1	2	3	4
41 Did you have a problem holding a pen, which made writing difficult?	1	2	3	4
42 Did you have difficulty manipulating small objects with your fingers (for example, fastening small buttons)?	1	2	3	4
43 Did you have difficulty opening a jar or bottle because of weakness in your hands?	1	2	3	4
44 Did you have difficulty walking because your feet dropped downwards?	1	2	3	4

Please go on to the next page

During the past week :

	Not at All	A Little	Quite a Bit	Very Much
45 Did you have difficulty climbing stairs or getting up out of a chair because of weakness in your legs?	1	2	3	4
46 Were you dizzy when standing up from a sitting or lying position?	1	2	3	4
47 Did you have blurred vision?	1	2	3	4
48 Did you have difficulty hearing?	1	2	3	4

Please answer the following question only if you drive a car

49 Did you have difficulty using the pedals?	1	2	3	4
--	---	---	---	---

Please answer the following question only if you are a man

50 Did you have difficulty getting or maintaining an erection?	1	2	3	4
--	---	---	---	---

Appendix II: Patient Global Impression of Change

1. Since starting this study, my *overall quality of life* is: (please circle one)

-3 Very much worse	-2 Moderately worse	-1 A little worse	0 About the same	1 A little better	2 Moderately better	3 Very much better
--------------------------	---------------------------	-------------------------	------------------------	-------------------------	---------------------------	--------------------------

2. Since starting this study, the numbness, tingling or pain in my hands and/or feet is: (please circle one)

-3 Very much worse	-2 Moderately worse	-1 A little worse	0 About the same	1 A little better	2 Moderately better	3 Very much better
--------------------------	---------------------------	-------------------------	------------------------	-------------------------	---------------------------	--------------------------

3. Would you recommend this therapy, to try to prevent or treat neuropathy, to other patients with problems similar to yours?

- No
- Yes
- Unsure

Comments:

Appendix III: Chemotherapy Induced Peripheral Neuropathy Assessment Tool (Quantitative Items)

Over the last week, how much have your neuropathy symptoms interfered with:	Not at all										Completely Interfering											
	0	1	2	3	4	5	6	7	8	9	10	0	1	2	3	4	5	6	7	8	9	10
Dressing (buttoning, zipping, etc)	0	1	2	3	4	5	6	7	8	9	10	0	1	2	3	4	5	6	7	8	9	10
Walking	0	1	2	3	4	5	6	7	8	9	10	0	1	2	3	4	5	6	7	8	9	10
Picking up objects	0	1	2	3	4	5	6	7	8	9	10	0	1	2	3	4	5	6	7	8	9	10
Holding onto objects	0	1	2	3	4	5	6	7	8	9	10	0	1	2	3	4	5	6	7	8	9	10
Driving	0	1	2	3	4	5	6	7	8	9	10	0	1	2	3	4	5	6	7	8	9	10
Working	0	1	2	3	4	5	6	7	8	9	10	0	1	2	3	4	5	6	7	8	9	10
Participating in hobbies or leisure activities	0	1	2	3	4	5	6	7	8	9	10	0	1	2	3	4	5	6	7	8	9	10
Exercising	0	1	2	3	4	5	6	7	8	9	10	0	1	2	3	4	5	6	7	8	9	10
Sleeping	0	1	2	3	4	5	6	7	8	9	10	0	1	2	3	4	5	6	7	8	9	10
Sexual activity	0	1	2	3	4	5	6	7	8	9	10	0	1	2	3	4	5	6	7	8	9	10
Relationships with other people	0	1	2	3	4	5	6	7	8	9	10	0	1	2	3	4	5	6	7	8	9	10
Writing	0	1	2	3	4	5	6	7	8	9	10	0	1	2	3	4	5	6	7	8	9	10
Usual household chores	0	1	2	3	4	5	6	7	8	9	10	0	1	2	3	4	5	6	7	8	9	10
Enjoyment of life	0	1	2	3	4	5	6	7	8	9	10	0	1	2	3	4	5	6	7	8	9	10

Appendix IV: Peripheral Neuropathy Question

1. How much of a problem has tingling or pain in your fingers and/or toes been in the past week?

0 **1** **2**

No tingling or pain
in fingers and/or
toes

3

4

5

6

7

8

9

10

[figure not shown]
Tingling or pain in
fingers and/or toes
as bad as you can
imagine

DRAFT

Appendix Va: Symptom Experience Diary –Baseline

Please circle **ONE** number for each item that best describes you over the past 7 days.

1. Over the past week, please rate your quality of life:

2. Do you have any skin rash on your hands or feet:

[figure not shown]

DRAFT

Appendix Vb: Symptom Experience Diary —During Treatment

Please circle **ONE** number for each item that best describes you over the past 7 days.

1. Over the past week, please rate your quality of life:

2. Do you have any skin rash on your hands or feet:

3. How many doses of the study medication do you think that you missed over the past week?
(Circle one answer)

0 times 1-2 times 3-4 times More than 5 times

4. Did you have any skin side effects from the study product?

No

Yes, if so, please describe the symptom(s) and severity:

5. Did you have any other side effects from the study product?

No

Yes, if so, please describe the symptom(s) and severity:

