4.0 Test Schedule

4.1 Test schedule for Chemotherapy-Induced Peripheral Neuropathy

Study Visit	1	2	3	4	5	6	7
Study Time Point	Screening /Baseline (Day -30 to Day 1)	Day 1	End of Week 1	End of Week 2 ^c (+3 Days)	End of Week 3	End of Week 4	End of study
CLINICAL ASSESSMENTS							
Informed consent	X						
Inclusion/exclusion criteria	X ^g						
Demographics/ Medical history	X						
Pregnancy testing ^a	X						
Randomization	X						
Dispense Study Product/Placebo		X		X			
Collect questionnaires							X
Adverse event assessment ^b			X	X	X	X	
STUDY TESTING							
EORTC QLQ-CIPN 20 instrument (Appendix I)	X		X	X	X	X	
Global impression of change (Appendix II)			X	X	X	X	
Chemotherapy Induced Peripheral Neuropathy Assessment Tool (Appendix III)	X		X	X	X	X	
Symptom experience diary (Appendix Va & Vb)	X ^d		X ^e	X ^e	X ^e	X ^e	
NCI-CTCAE neuropathy scale ^f (Appendix VI)	X		X	X	X	X	
Cycle = 14 days							
^a For individuals of childbearing potential. Must be done \leq 7 days prior to registration.							
^b Research nurse or clinician to call patient. Including inquiry about skin toxicity and to assess for suicidal thoughts (Appendix IX). Ask the patient if they have missed any doses of the study							

medication and provide education if necessary. Note any other pertinent information that the patient provides.

^c After subject completes week 2 they will turn in completed questionnaire diary and start the next supply of cream within 1-3 days after completing the first 2 weeks, ideally.

^d Appendix Va: System Experience Diary used for baseline assessment. Must be completed prior to application of study medication.

^e Appendix Vb: System Experience Diary used for weekly assessments. Must be completed at the end of each week.

^f To be completed during research nurse or clinician call to patient per Appendix VI.

^g Required Initial Laboratory Values per inclusion criteria 3.19c can be done any time after the patient has completed their chemotherapy and prior to study registration.

5.0 Stratification Factors:

- Gender (Male, Female, or Other)

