7.0 Protocol Treatment

7.1 Treatment Plan:

Patients will be instructed to apply the CBD or placebo cream in a thin layer (approximately 4-5 pumps of product) to affected areas twice daily for 14 days.
CIPN in hands: apply 4-5 pumps to hands twice a day
CIPN in feet: apply 4-5 pumps to feet twice a day
After two weeks of using the designated treatment participants will cross over to the other treatment. The other treatment will be applied as described above, twice daily for another two weeks.

7.2 Breaking Code:

During the study, codes should only be broken in emergency situations, which are not expected in this study. In the event of an emergency, call the MCCC Registration Office at [REDACTED] to break the code on Monday through Friday, 8:00 a.m. to 4:30 p.m. Central Time. Alternatively, email the Registration Office [REDACTED]. If the code must be broken after hours, assume the patient was assigned to active treatment and treat accordingly. Place a call to the MCCC Registration Office and leave a message informing them of the need to un-blind a patient. Provide your contact information so that MCCC Registration Office personnel can return the call the next business day.

7.3

After the patient has completed the study and the questionnaires have been completed and sent in, the code can be broken, so that the patient can choose whether to continue to use CBD on their own if they felt it gave them benefit. To do this, the MCCC Registration

Office may [REDACTED] to find out which study therapy the patient was receiving.

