16.2 Analysis Plan for Secondary Outcome and Translational Endpoint

Analyses for secondary endpoints will also be descriptive in nature. Due to the exploratory nature of this research, we will not adjust for multiple comparisons for the secondary analyses. Analyses of the motor and autonomic subscales will be identical to the analyses of the primary endpoint. Analyses of CTCAE grades and the symptom questionnaire individual items will compare the incidence and maximum (worst) values between arms. Fisher's exact tests will be used to compare incidence rates and Wilcoxon rank-sum tests will be used to compare maximum values between arms.

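### The weekly missed-dose item in the during-treatment diary has no answer for exactly five missed doses

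*Combined protocol and SAP*

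**What the plan says.** The during-treatment diary in Appendix Vb asks, as item 3, "How many doses of the study medication do you think that you missed over the past week", with the instruction "Circle one answer". The printed options are "0 times 1-2 times 3-4 times More than 5 times".

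The test schedule in section 4.1 gives the diary at the end of weeks 1, 2, 3 and 4, and its footnote states: "Must be completed at the end of each week". Section 7.1 has cream applied "to affected areas twice daily for 14 days", and the same twice-daily schedule is listed separately for hands and for feet. After 14 days the patient crosses to the other cream on the same schedule.

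Two other places bear on the item:

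- **Section 16.2.** The secondary analysis plan says: "Analyses of CTCAE grades and the symptom questionnaire individual items will compare the incidence and maximum (worst) values between arms". It adds: "Fisher's exact tests will be used to compare incidence rates and Wilcoxon rank-sum tests will be used to compare maximum values between arms". It neither names nor excludes the missed-dose item.
- **Section 4.1, footnote b.** At each weekly call the research nurse or clinician is told: "Ask the patient if they have missed any doses of the study" medication. No count or category is prescribed for the answer.

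**The concern.** A single-choice item should give every possible count one and only one category. This one skips a count, and the gap lies between the two highest categories, where adherence is poorest. Five is not an exotic value. Sections 8.0 and 16.32 provide for patients to stop the cream because of side effects, and section 8.0 hopes they will still complete questionnaires. For example, a patient who stops after the morning application on day 5 of a diary week, and counts what was not applied afterwards, misses one application that day and four over the next two days, which makes five.

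What is at stake is the record of adherence. The pilot is meant to inform a phase III trial, and a small or absent difference between creams is hard to interpret without knowing how much cream was applied. If the item also enters the between-arm comparison of section 16.2, the gap affects a planned analysis as well as a descriptive summary.

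**Working it through.** **The plan's own figure.** The only computed design figures are the powers in section 16.1. For effect size 0.9, 20 per arm and two-sided alpha 0.05, a noncentral t with 38 degrees of freedom and noncentrality 0.9 × √(20/2) = 2.85 gives 0.792, against the stated 0.79. The missed-dose item does not enter this calculation, so nothing below changes it.

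**Coverage of the options.** Inputs: two application times a day (section 7.1) and a seven-day recall (Appendix Vb), so 2 × 7 = 14 application times and possible counts from 0 to 14.

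| Option | Counts covered |
|---|---|
| first | 0 |
| second | 1, 2 |
| third | 3, 4 |
| fourth | 6 to 14 |
| none | 5 |

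Five is the only uncovered count.

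**What five means.**

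- One dose per application time: 5/14 = 35.7%. The neighbouring counts are 4/14 = 28.6% and 6/14 = 42.9%.
- Hands and feet counted separately by a patient treating both: 2 × 14 = 28 applications a week, and 5/28 = 17.9%. The possible counts then run to 28, and five is still the only one without a category.

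**How often it might occur.** The documents give no miss rate. As an illustration only, assume each of 14 applications is missed independently with probability p. Then P(exactly 5) = C(14,5) p⁵ (1 − p)⁹, with C(14,5) = 2002. Forty patients with four diaries each give 160 patient-weeks.

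| Assumed p | P(exactly 5) | Expected among 160 |
|---|---|---|
| 5% | 0.0004 | 0.1 |
| 10% | 0.008 | 1.2 |
| 20% | 0.086 | 14 |
| 30% | 0.196 | 31 |

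The range is wide because p is unknown. Real misses are also likely to cluster within patients, which this model ignores.

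**Effect on the tests in section 16.2, if the item is included.** Compare each possible response of a patient who missed five with the result had the last option been five or more.

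- *Circles the top option:* same top category, so the same rank in the Wilcoxon test and the same any-versus-none status in Fisher's test.
- *Circles the third option:* incidence is unchanged. The worst value is one category too low, unless another diary in the same comparison already reached the top.
- *Leaves it blank:* the worst value is too low or missing, with the same exception. Incidence changes only if no other diary in the comparison records a miss.

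**The case against.** The strongest reply is that this is a proofreading slip with almost no analytic reach, and much of that stands.

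- **Section 16.2 does not name the item.** A reader might infer that the plan puts missed doses into the arm comparison. It says only that symptom-questionnaire items are compared. The diary is the instrument that fits, but item 3 measures adherence, and sections 2.2 and 16.1 describe the symptom questionnaires as a source for adverse event profiles. The link is a possible reading, and no adherence analysis, per-protocol set or adherence threshold is defined anywhere.
- **Misclassification is not inevitable.** A reader might infer that such a patient must be misclassified. The patient may instead leave the item blank, and the question asks for an estimate from memory in coarse bands.
- **No adherence boundary lies at five.** A reader might take five as the line between acceptable and poor adherence. The documents set no such line.
- **It is not the only source.** The weekly call also asks about missed doses, which is a partial check without a set format. The accountability logs in section 15.11 track product and describe no count of applications.
- **More than a third missed is conditional.** It holds for 14 doses a week and falls to 18% if the two sites are counted separately.

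These points limit the weight of the defect. They do not remove it: the form still cannot record one true answer, and the options are printed as running text with no sign of a missing figure or redaction.

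**Conclusion.** The point holds as a minor defect in a data-collection form. Item 3 offers no valid answer for exactly five missed doses, so that answer will be wrong or missing when it arises. This conclusion rests only on the printed options.

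Its size depends on two things the documents leave open: what a patient counts as a dose, and how often five occurs. The number of patients affected is unknown and probably small. Any effect on a planned test requires reading section 16.2 to include the item. Even then it is confined to the boundary between the two highest categories for worst values, apart from a blank in a patient with no other recorded miss. The primary endpoint, the sample size and the power table are untouched, and the secondary analyses are declared descriptive and unadjusted for multiplicity.

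**What to change.** Change the last option of item 3 to five or more times, in the diary pages for weeks 1 to 4. Every count then falls in exactly one category. The cost is a short edit to one form, with no effect on sample size or analysis method.

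If booklets are already in use, add a written data-handling note saying how an answer of five, or a blank on this item, is to be coded, and record which form version each patient completed. One sentence in section 16.2 saying whether item 3 is among the items compared between arms would settle the remaining ambiguity at no cost.

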2.1 Primary Objective

The aims of the proposed project include:

1. To evaluate whether topical CBD improves chemotherapy-induced peripheral neuropathy (CIPN), compared to placebo
2. To evaluate side effects from topical CBD cream use, compared to placebo

The data obtained from this trial are designed to provide information to allow for a larger phase III, placebo-controlled, randomized, clinical trial.

Primary endpoint

The primary endpoint is change in CIPN from baseline to the end of week 2. CIPN will be measured by the sensory subscale of the EORTC QLQ-CIPN20 which is composed of 9 individual items.

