2.2 Secondary Goals

Secondary endpoints include other measures of neuropathy as measured by the EORTC QLQ CIPN20 motor subscale, the EORTC QLQ CIPN20 autonomic scale, and the total CTCAE neuropathy scale. Adverse event profiles will also be assessed using symptom questionnaires and CTCAE v5.0.

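### Low-grade non-skin side effects have no general attribution-free route into the placebo comparison: diary item 5 asks only about effects the patient blames on the cream

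*Combined protocol and SAP*

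**What the plan says.** Section 2.1 lists two aims under the primary objective. The second is "To evaluate side effects from topical CBD cream use, compared to placebo". Section 2.2 names the data sources: "Adverse event profiles will also be assessed using symptom questionnaires and CTCAE v5.0". Section 16.1 repeats this, and Section 16.2 gives the analysis: "Analyses of CTCAE grades and the symptom questionnaire individual items will compare the incidence and maximum (worst) values between arms". For incidence, "Fisher's exact tests will be used to compare incidence rates".

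The weekly diary in Appendix Vb has three items on symptoms or side effects:

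- Item 2: "Do you have any skin rash on your hands or feet". No cause is asked, and the baseline diary (Appendix Va) has the same item.
- Item 4: "Did you have any skin side effects from the study product".
- Item 5: "Did you have any other side effects from the study product".

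Outside the diary, Section 10.62 assigns all other adverse events to the weekly calls by the research nurse or clinician. Grade 3 and 4 events go on the case report form regardless of attribution. Grade 2 events go on it only when judged at least possibly related, and grade 1 events are not listed. The same section says that the patient booklets will not be used for collecting and documenting adverse events. The call script in Appendix IX covers suicidal thoughts, skin irritation, and rash, blisters or open skin.

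**The concern.** In a randomised, blinded comparison the placebo arm does the work of attribution: the excess over placebo estimates what the drug causes. Asking each patient to decide cause first adds a filter that the design does not need, and patients may be poor judges of it. A symptom away from the hands or feet, such as tiredness or an upset stomach, may not be connected with a cream. The answer to item 5 is then no, and the symptom is absent from the comparison in Section 16.2.

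The stake is modest but real. The pilot is meant to inform a phase III trial, and its second aim is side effects against placebo. Appendix VII reports no formal pharmacokinetic studies of this product and says that a very small amount may be absorbed systemically. Non-skin effects therefore cannot be ruled out in advance, and a complete low-grade tolerability profile is something a pilot can usefully supply.

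**Working it through.** **Step 1: is there a figure to reproduce?** Not for side effects. The only power figures, in Section 16.1, concern the CIPN20 sensory score. A noncentral t calculation (20 per arm, two-sided 0.05) reproduces them, for example 0.792 against the stated 0.79 at an effect size of 0.9. They do not bear on this point. The check is therefore to trace each kind of event to the arm comparison.

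**Step 2: routes into the comparison.**

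| Kind of event | Route | Is attribution needed? |
|---|---|---|
| Skin, any grade | Diary item 2; Appendix IX skin questions | No |
| Any event, grade 3-4 | Case report form (10.62) | No |
| Serious event with hospitalisation, any grade | Expedited report (10.41), also reported routinely (10.1) | No |
| Symptoms listed in the CIPN20 (e.g. dizziness, blurred vision) | Appendix I, weekly | No |
| Suicidal thoughts | Appendix IX | No |
| Other non-skin, grade 2, not serious | Case report form (10.62) | Yes, judged at least possibly related |
| Other non-skin, grade 1 | Not listed in 10.62 | No case report form route |
| Other non-skin, any grade | Diary item 5 | Yes, by the patient |

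The grade 1 and grade 2 rows are the gap. The weekly call is meant to cover other adverse events, but Appendix IX scripts no general symptom question. Whatever is mentioned must still pass the grade and relatedness rule in 10.62.

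**Step 3: does the role of the booklets change this?** Under Sections 2.2, 16.1 and 16.2 the diary is analysed, and the patient's attribution is the filter. If 10.62 is taken to exclude the booklets from the adverse event comparison, the diary drops out and the relatedness rule is the filter. The gap remains on either reading. The reason that 10.62 gives is that booklets are collected only at the end of the study. That also sits awkwardly with Section 6.4b, where the first treatment booklet is mailed back at the end of week 2.

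**Step 4: can the effect on the comparison be sized?** No, as one assumed set of rates shows. Suppose 40% of patients in each arm have an unrelated symptom, CBD independently causes a symptom in 30%, and there are 20 patients per arm.

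- True incidence on CBD: 1 − (1 − 0.30)(1 − 0.40) = 58%; on placebo: 40%.
- If patients attribute a share c of caused and b of unrelated symptoms, recorded incidence on CBD is 1 − (1 − 0.30c)(1 − 0.40b); on placebo it is 0.40b.

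| Question asked | CBD | Placebo | Difference | Fisher power (two-sided 0.05) |
|---|---|---|---|---|
| Any symptom, no cause (c = b = 1) | 58% | 40% | 18 points | 12% |
| Attributed only, c = b = 0.5 | 32% | 20% | 12 points | 8% |
| Attributed only, c = 0.8, b = 0.1 | 27% | 4% | 23 points | 41% |

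With the same underlying truth, the filter shrinks the difference when attribution is indiscriminate and enlarges it when attribution is accurate. The documents give none of these rates, so neither the size nor the sign of the distortion can be stated.

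**The case against.** The strongest reply is that an attribution question is not simply a loss. Patients who have had chemotherapy may have many background symptoms, and these dilute a comparison of 20 against 20. The last row of the table above shows that a good filter can help. This stands. A reader might infer that the wording can only discard drug effects and so must make CBD look cleaner. The documents do not support that, and they do not support replacing the attributed answer outright.

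A second reply is that the safety comparison has several other routes. This also stands, and it sets the limits of the point. A reader might infer that the whole side-effect comparison misses unattributed effects. It does not: skin effects, grade 3-4 events, serious events with hospitalisation and the CIPN20 symptoms are captured without attribution. Rewording item 4 would add little.

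A reader might also think that in weeks 3 and 4 the study product could mean either cream. The diary's 7-day window, its completion at the end of each week, and the dispensing of one supply at a time largely settle this. A lingering effect of the first cream would come from the absence of a washout, not from the wording.

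Finally, the trial is a descriptive pilot with exploratory testing, and asking about effects of the product is close to the literal aim. That lowers the importance of the point. It does not answer it, because an aim framed against placebo is best served by recording symptoms in both arms before cause is judged. Section 10.62 can also be read as limiting only what goes on adverse event forms, leaving the diary as separate patient-reported data. If that is what is meant, the plan should say so.

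**Conclusion.** The point holds in a narrow form. Apart from the symptoms in the CIPN20 and the scripted question on suicidal thoughts, non-serious grade 1-2 non-skin effects have no attribution-free route into the comparison with placebo. In the diary the filter is the patient's opinion. On the case report form it is a relatedness judgement for grade 2, and grade 1 is not listed. The consequence is a possibly incomplete low-grade tolerability estimate to carry into phase III planning. It is not an error in a confirmatory test, and no figure in the plan is wrong.

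The conclusion about the gap rests only on the text of Sections 10.62 and 16.2 and Appendices I, Vb and IX. The rates in the working are assumptions, used solely to show that the size and direction are unknown. This is a cheap improvement to the form. The differing roles given to the booklets in Section 10.62 and in Sections 2.2, 16.1 and 16.2 should be reconciled in any case.

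**What to change.** 1. In Appendix Vb, reword item 5 to ask about any other new or worse symptom in the past 7 days, without reference to cause. Keep the free-text description and severity.
2. Add a follow-up tick: does the patient think it was due to the cream used that week?
3. In Section 16.2, state that both the all-symptom incidence and the attributed incidence will be reported by arm.
4. Reconcile Section 10.62 with Sections 2.2, 16.1 and 16.2: say whether the diaries feed the adverse event profile or are a separate patient-reported summary. Align the stated time of booklet collection with Section 6.4b.

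The cost is an edit to one form page and a few sentences of plan text. The present information is kept through the attribution tick. The downside is that unrelated background symptoms will be recorded in both arms and may dilute the all-symptom comparison, which is why the attributed version should be reported beside it.
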